7.8.1.5 Events qualifying for external adjudication by the adjudication committee

An independent external CEC regularly reviews events and evaluates whether pre-specified criteria for these adjudication endpoints are met. Details on composition of the CEC, responsibilities and clinical event definitions are provided in the separate CEC Charter.

Adjudication assessments will be incorporated into the database.

Details of the adjudication process are described in the CEC charter.

Hepatic adverse events:

Frequency tables summarising the relatedness and severity will be provided, including a listing showing the trigger events and adjudication results. This will include all adjudicated events up to 30 days after treatment stop.

Ketoacidosis:

Frequency tables showing adjudicated certain ketoacidosis will be provided, including a listing showing the trigger events and adjudication results. This will include all adjudicated events up to 7 days after treatment stop.

7.8.1.6 AEs while patients taking wrong medication

A listing will be provided for AEs that occurred while a patient was taking the wrong study medication.

If such a patient is identified an additional adverse event table that assigns the adverse events to the actual treatment taken will be presented. A patient who took both the assigned treatment and also at least one tablet of the wrong treatment will be counted as at risk in both treatment groups for the respective relevant time. The table will include all adverse events by SOC and PT.

7.8.1.7 Adverse event incidence rates

For AE tables showing patients with events, in addition to the frequency tabulations, time-adjusted adverse event analyses will be performed for all AEs, investigator defined drug-related AEs, AEs leading to discontinuation, serious AEs, and adverse events of special interest by SOC and PT or High-Level Term (HLT) and PT, respectively.

The time at risk in patient years for the on-treatment phase is derived as follows:

Patients with AE:

time at risk (AE) in days = date of start of AE with specified PT/SOC/HLT – study treatment start date + 1

Patients without AE:

time at risk (AE) in days = end date of time at risk – study treatment start date + 1, where end date of time at risk is the minimum of date of last study drug intake + x days and date of death, if applicable.

The standard approach will be x=7 days, but for certain AESIs in addition other approaches will be used.

Total AE-specific time at risk per treatment group is then derived as:

Time at risk (AE) [years] = Sum of time at risk [days] over all patients in a treatment group / 365.25

For 'each row of a table' (e.g. displaying an SOC), time at risk is calculated using start of first AE summarised in this row; e.g. for patient with AE in a specified SOC, time at risk = date of start of AE with specified PT in this SOC – start of study treatment + 1.

The AE incidence rate per 100 patient years will then be calculated as follows:

Incidence rate per 100 patient years (pt-yrs) = $100 * \text{number of patients with AE} / \text{time at risk (AE) [years]}$.

In a similar way the time at risk and incidence rate for the post-treatment period is derived. Hereby the start date is the start date of the post-treatment phase instead of the study treatment start date.

For some specific outputs showing number of episodes, event rates will be defined as number of episodes divided by time at risk. Time at risk will be end date of time at risk – study treatment start date + 1, where end date of time at risk is the minimum of date of last study drug intake + x days and date of death, if applicable.

7.8.2 Laboratory data

Standard safety tables will not include eGFR or creatinine. Analyses for eGFR and creatinine will be done separately.

For continuous safety laboratory parameters, normalised values will be derived as well as the differences to baseline. The process of normalisation as well as standard analyses for safety laboratory data are described in the BI guidance for the Display and Analysis of Laboratory Data ([BI-KMED-BDS-HTG-0042 \(4\)](#)). All analyses considering multiple of times upper limit of normal (ULN) will be based on original and not normalised data.

Laboratory parameters will be shown in conventional units. Where conventional units differ from SI units, analyses will be repeated on SI units.

The analyses of laboratory data will be descriptive in nature and will be based on BI standards [see Data Management and Statistics Manual (DM&SM): Display and Analysis of Laboratory Data ([BI-KMED-BDS-HTG-0042 \(4\)](#))].

Laboratory measurements taken up to 3 days after the last administration of randomised study drug will be considered as on-treatment.

Default settings will be used for repeated values (using closest and then worst value).

Laboratory values will be compared to their reference ranges and frequency tables will be provided for the number of patients within and outside the reference range at baseline and the last measurement on treatment. Descriptive statistics will be provided by treatment group for baseline, last value on-treatment and for changes from baseline to last value on treatment. For semi-quantitative or categorical laboratory values, shift tables for baseline and last value on treatment will also be provided. Frequency tables will summarise the number of patients with potentially clinically significant abnormalities.

Additionally, for urine ketones a shift table of baseline vs value at visit for each visit will be shown.

For the table on potentially clinically significant abnormalities only patients with at least one available on-treatment value will be included in the analysis of an individual laboratory parameter. Other tables are comparing baseline to on-treatment values and will only include patients with a baseline value and at least one available on-treatment value. All individual data will be presented in listings.

To support analyses of liver-related adverse drug effects, patients with Aspartate transaminase (AST) and/or Alanine transaminase (ALT) $\geq 3 \times \text{ULN}$ with concomitant or subsequent Total Bilirubin (TBILI) $\geq 2 \times \text{ULN}$ in a 30 day period after AST/ALT elevation are of special interest. In addition, of these cases, it will be considered whether the alkaline phosphatase (AP) is less than 2 x ULN (maximum value in a 30 day period after AST/ALT elevation) or not. The start of the 30-day time span is triggered by each liver enzyme elevation above the defined thresholds. Patients who fulfil one or two of the criteria for ALT/AST or total bilirubin elevations above and have no information available for the remaining parameter(s) within the 30 day time window will not be listed under “ALT and/or AST $\geq 3 \times \text{ULN}$ with TBILI $\geq 2 \times \text{ULN}$ ”.

In addition ALT/AST will be used to investigate elevated liver enzymes:

- ALT/AST $\geq 3 \times \text{ULN}$
- ALT/AST $\geq 5 \times \text{ULN}$
- ALT/AST $\geq 10 \times \text{ULN}$
- ALT/AST $\geq 20 \times \text{ULN}$

All liver enzyme elevations within 30 days of treatment discontinuation will be shown.

Frequency tables of patients with elevated liver enzymes defined by ALT and/or AST, total bilirubin and AP combinations will be provided. Details on patients with elevated liver enzymes will be listed.

For the following parameters:

- eGFR,
- creatinine (only descriptive),

the time course of changes will be assessed. The analysis will be performed by applying MMRM models to OC-OT data on the treated set. The MMRM models that will be used are specified in [Section 7.6](#). These analyses will be conducted on data before any normalisation. The MMRM analyses will also be shown graphically.

For the following parameters:

- haemoglobin, and
- haematocrit

the change from baseline will be assessed. The analysis will be performed by applying ANCOVA models to OC-OT data on the treated set. The ANCOVA model will include treatment and baseline as fixed effects. These analyses will be conducted on data before any normalisation.

To support analysis of renal function, eGFR throughout the trial will be categorised according to the following Chronic Kidney Disease (CKD) staging ([Table 7.8.2: 1](#)): All calculations for the staging of renal function will be based on the originally measured laboratory values, not on normalised values with BI standard reference ranges.

For the following parameters measured at the follow-up visit, additionally descriptive statistics at baseline, last value on treatment and follow-up will be provided for patients with valid measurements at all three timepoints.

- creatinine
- eGFR
- haematocrit
- haemoglobin

Table 7.8.2: 1 CKD staging

| Stage | eGFR (mL/min/1.73m²) | Description | Label for displays | Additional labels# |
|--------------|--|--------------------------------------|-------------------------------|----------------------------------|
| 1 | ≥90 | Normal or high | ≥90 | ≥90 (CKD 1) |
| 2 | 60 to <90 | Mildly decreased | 60 to <90 | 60 to <90 (CKD 2) |
| 3A | 45 to <60 | Mildly to moderately decreased | 45 to <60 | 45 to <60 (CKD 3a) |
| 3B | 30 to <45 | Moderately to severely decreased | 30 to <45 | 30 to <45 (CKD 3b) |
| 4 | 15 to <30 | Severely decreased | 15 to <30 | 15 to <30 (CKD 4) |
| 5 | <15 | Kidney failure | <15 | <15 (CKD 5) |

A shift table from baseline to last value on treatment and to minimum value on treatment for eGFR (CKD-EPI)_{cr} will be provided.

7.8.3 Vital signs

Heart rate over time will be summarised descriptively based on OC-OT on the treated set. Descriptive statistics will also be shown graphically.

Additionally descriptive statistics at baseline, last value on treatment and follow-up for patients with valid measurements at all three timepoints will be shown.

7.8.4 ECG and physical examination

Clinically relevant abnormalities found at physical examination will be considered to have already existed prior to signing of informed consent and therefore should be considered baseline conditions instead of adverse events, unless there is good reason to assume that they first appeared after signing of consent.

Outcomes of ECGs will be part of the reporting of medical history or AE reporting. Categorical findings as collected in the eCRF will also be summarised descriptively.

7.8.5 Others

Not applicable

9. ADDITIONAL SECTIONS

9.1 REGIONS AND COUNTRIES

Countries will be assigned to regions, as outlined in [Table 9.1: 1](#).

Table 9.1: 1 Regions and countries

| Region | Country |
|---------------|---|
| Australia | Australia |
| Europe | Germany Greece Italy Norway Poland Portugal Spain Sweden |
| North America | Canada US |

9.2 DIABETES STATUS AT BASELINE

Patients will be assigned to diabetes status category, as outlined in [Table 9.2:1](#).

Table 9.2: 1 DM at baseline

| Diabetes status at baseline | Definiton |
|------------------------------------|---|
| DM | 
Patients who fulfil one of the following:
 
 - investigator-reported medical history of diabetes on the medical history page 
OR
 
 - any pre-treatment HbA1c value $\geq 6.5\%$ |
| Pre-DM | 
Patient who fulfil all of the following:
 
 - investigator reported 'no' for the medical history of diabetes on the medical history page 
AND
 
 - a pre-treatment HbA1c value of $\geq 5.7\%$ and all pre-treatment HbA1c $< 6.5\%$ |
| Missing | 
Patients who fulfil one of the following:
 
 - missing assessment of history of diabetes on the medical history page AND all pre-treatment HbA1c $< 6.5\%$ 
OR
 
 - no pre-treatment measurement of HbA1c AND investigator reported 'no' for the medical history of diabetes on the medical history page 
OR
 
 - no pre-treatment measurement of HbA1c and missing assessment of history of diabetes on the medical history page |
| Non-DM (excl pre-DM) | Patients not meeting the above criteria |

9.3 DERIVATION OF RESPONDER THRESHOLD FOR KCCQ-TSS AND CHQ-SAS DYSPNEA

A minimal clinically meaningful within patient-change in scores (i.e. responder threshold) will be estimated from the trial population (both treatment groups pooled) for KCCQ-TSS and CHQ-SAS Dyspnea using the below algorithm. All observed values will be considered in this analysis without imputation of missing values (OC-AD).

Anchor

The Patient Global Impression of Severity (PGI-S) of Dyspnea and PGI-S of Heart Failure Symptoms will each be used as the primary anchor for the CHQ-SAS Dyspnea scale and KCCQ-TSS, respectively. The Patient Global Impression of Change (PGI-C) of Dyspnea and PGI-C of Heart Failure Symptoms will be considered as secondary anchor scales for the CHQ-SAS Dyspnea scale and KCCQ-TSS, respectively.

A minimal clinically meaningful improvement for each PGI-S scale will be considered to be at least a one category improvement in change from baseline in PGI-S at week 12.

A minimal clinically meaningful improvement for each PGI-C scale will be considered to be at least “a little better” in PGI-C at week 12.

As an ancillary consideration, the distance walked in 6 minutes will be evaluated as a clinical indicator of patient improvement as well. Patients who improve at least 30 meters from baseline in distance walked in 6 minutes will be considered to be clinical responders [[R17-1227](#)] (5).

Responder Threshold

To determine the threshold of the Patient Reported Outcome (PRO) measure that best identifies patients with minimal clinically meaningful difference as specified above (responders / non-responders), the following procedure will be applied:

A receiver operating characteristic (ROC) curve of change from baseline of the PRO measure will be derived from the logistic regression model with the binary anchor (at least one category improvement in PGI-S Y/N) as dependent variable.

The mean of the cut-offs closest to the balance point (i.e. where sensitivity equals specificity) will be used as the responder threshold for each respective scale’s PRO score.

For further analysis of the key secondary endpoint as defined in [Section 7.5.1.4](#) a patient will be considered a responder if the PRO score is greater than or equal to the response threshold determined by the anchor of one category improvement in corresponding PGI-S questionnaire.

Graphical presentations

The ROC curve will be used to illustrate the ability of the PRO score to discriminate between responders and non-responders. The area under the ROC curve (AUC) will be reported in addition.

Descriptive empirical cumulative distribution functions (ECDF) will also be plotted by each anchors categories for each PRO.

Supportive Analyses

Distribution-based analyses will be performed for the CHQ-SAS Dyspnea scale and the KCCQ-TSS on data of change from baseline to week 12 to support the responder definition as defined above.

One standard error of measurement (SEM) as well as $0.2*SD$ and $0.5*SD$ of the CHQ-SAS Dyspnea scale and the KCCQ-TSS baseline measurement will be used as benchmarks [R07-1182](6).

The SEM is defined as $SD * \sqrt{(1 - r)}$ with reliability coefficient $r=0.88$ for the KCCQ-TSS (Cronbach's alpha in [R17-2666] (7)) and $r=0.91$ for the CHQ-SAS Dyspnea (Cronbach's alpha in [R17-2917] (8)).

For patients who achieved a one-category improvement in PGI-S Dyspnea at week 12 from baseline, the descriptive median (with inter-quartile range) of CHQ-SAS Dyspnea will be displayed by baseline PGI-S Dyspnea category. The table will be repeated separately for one-category deterioration, two-category improvement, two category deterioration, and no change in PGI-S dyspnea.

For patients who achieved a one-category improvement in PGI-S in heart failure symptoms at week 12 from baseline, the median (with inter-quartile range) of KCCQ-TSS will be displayed by baseline PGI-S in heart failure symptoms category. The table will be repeated for one-category deterioration, two-category improvement, two category deterioration, and no change in PGI-S in heart failure symptoms.

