5.1.3 Chronic Heart Failure Questionnaire Self Administered Standardized

The CHQ-SAS is a heart failure-specific PRO measure that assesses the patients' perception of their heart failure and measures the impact of heart failure symptoms. The CHQ-SAS refers to the CHQ-self-administered format and contains 16 standardised questions pertaining to 3 domains: dyspnea, fatigue and emotional function. Items are rated on a 7-point Likert scale ranging from 1 (e.g. extremely short of breath) to 7 (e.g. not at all short of breath) [[R17-2969](#)].

Patients will complete the first administration of the questionnaire at Visit 2 and complete the follow-up administration questionnaire at Visits 3 and 4 and early discontinuation (if applicable).

Please refer to [section 6.2.2](#) for order of completion of patient reported outcome measures.

Please refer to [appendix 10.3.2](#) for the first administration of the questionnaire and the ISF for the follow-up administration of the questionnaire.

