7.5.1.4 Further exploratory analyses of the key secondary endpoints

A minimal clinically meaningful within-patient change in scores (i.e. responder threshold) will be estimated from the trial population (both treatment groups pooled) for KCCQ-TSS and CHQ-SAS dyspnea as described in [Appendix 9.3](#).

A responder analysis using a chi-square test will be evaluated in addition. The response threshold will be determined as defined in [Appendix 9.3](#).

An empirical cumulative distribution function of descriptive change from baseline to week 12 by treatment group on OC-AD on the randomised set will be shown.

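### SAP 9.3 applies a change-from-baseline threshold to the PRO score itself: the responder sentence is wrong as written, the intended rule is recoverable, and only an exploratory analysis is affected

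*SAP*

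**What the plan says.** SAP 7.5.1.4, among the further exploratory analyses of the key secondary endpoints, says what the threshold is: "A minimal clinically meaningful within-patient change in scores (i.e. responder threshold) will be estimated from the trial population". SAP 9.3 opens with the same definition. The analysis that uses it is also in 7.5.1.4: "A responder analysis using a chi-square test will be evaluated in addition", with the threshold taken from Appendix 9.3.

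SAP 9.3 then gives the derivation: "A receiver operating characteristic (ROC) curve of change from baseline of the PRO measure will be derived from the logistic regression model", with a one-category improvement in PGI-S as the binary anchor. The cut-offs nearest to equal sensitivity and specificity are averaged, and the result "will be used as the responder threshold for each respective scale’s PRO score".

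The classification sentence follows: "a patient will be considered a responder if the PRO score is greater than or equal to the response threshold". It mentions neither change nor week 12.

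**The concern.** The threshold is on the change scale and the quantity compared with it is on the score scale. Elsewhere the SAP keeps these apart. Section 9.4 defines the KCCQ-TSS and CHQ-SAS dyspnea scores as values at an assessment, and separately defines change as the week-12 value minus the baseline value. Section 5.3 words the KCCQ and CHQ domain response as an improvement. A programmer who takes the scores from 9.4 and the rule from 9.3 would compare the week-12 score with a cut-off meant for a difference.

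For this analysis, that sentence is the only one that says who counts as a responder. The threshold is estimated from the trial's own data, so the rule that applies it should need no interpretation. Responder percentages are also readily quoted when PRO results are interpreted.

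**Working it through.** The documents give no responder rate, threshold value or power for this analysis, so there is no figure of the plan to reproduce on the point itself. The effects and SDs borrowed in step 4 come from Protocol 7.7.1, and its complete-data power figures do reproduce.

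**1. Check of the borrowed inputs.** With n = 150 per arm and two-sided 5%, P(X<Y) = Φ(−δ/(SD·√2)) and power = Φ(√(6n)·|p − 0.5| − 1.96).

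- KCCQ-TSS, δ = 5, SD 13: p = 0.393 and √900 = 30, giving 89.5% (stated 89%).
- SDs 15, 17 and 20 give 79.8, 69.5 and 55.8% (stated 79, 69 and 55%).
- CHQ dyspnea, δ = 0.5, SDs 1, 1.2 and 1.4 give 98.6, 93.5 and 84.9% (stated 98, 93 and 84%).

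All agree within 1 point.

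**2. CHQ-SAS dyspnea, literal rule (score ≥ T).** Protocol 5.1.3: "Items are rated on a 7-point Likert scale ranging from 1". SAP 9.4.2 takes the mean of the answered items among questions 1–5, and SAP 6.6.2 confirms a range of 1 to 7. A mean of values that are each at least 1 is at least 1. So for any T ≤ 1, 100% of scored patients in both arms are responders. The proxy T = 0.5 (the CHQ domain response in SAP 5.3) falls in this range. This needs no distributional assumption. With no non-responders, the chi-square statistic cannot be computed.

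For a larger threshold, T = 1.5, a normal distribution truncated to 1–7 with assumed mean 3.5–5.5 and SD 1–1.4 gives 96–100% responders.

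**3. KCCQ-TSS, literal rule.** The score runs from 0 to 100 (SAP 6.6.2). The documents give no week-12 distribution, so a normal distribution truncated to 0–100 is assumed, with mean m = 45–75 and SD s = 20–25 before truncation:

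P(score ≥ T) = 1 − [Φ((T−m)/s) − Φ((0−m)/s)] / [Φ((100−m)/s) − Φ((0−m)/s)]

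Lowest case, m = 45, s = 25, T = 20: 1 − [Φ(−1) − Φ(−1.8)] / [Φ(2.2) − Φ(−1.8)] = 1 − (0.1587 − 0.0359)/(0.9861 − 0.0359) = 0.871.

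| Threshold T | Share classed as responders |
|---|---|
| 5 | 98–100% |
| 10 | 95–100% |
| 20 | 87–100% |

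**4. Change-based rule, for comparison.** Take change ≥ T with T = 5 (KCCQ-TSS) or 0.5 (CHQ dyspnea), the Protocol 7.7.1 effects and SDs, normal changes and an assumed mean placebo change of 0. The placebo share is 1 − Φ(T/SD). The empagliflozin mean equals T, so its share is 50%.

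- KCCQ-TSS: SD 13 gives 1 − Φ(0.385) = 35%; SD 20 gives 1 − Φ(0.25) = 40%. Chi-square power at 150 per arm is about 75% down to 40%.
- CHQ dyspnea: SD 1 gives 1 − Φ(0.5) = 31%; SD 1.4 gives 1 − Φ(0.357) = 36%. Power is about 93% down to 69%.

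The change-based rule therefore leaves a real comparison, 31–40% against 50%. The literal rule leaves little or none.

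**The case against.** The best defence is that the section resolves its own slip. The threshold is twice defined as a within-patient change, in 7.5.1.4 and at the start of 9.3, so only a change can sensibly be compared with it. The graphical paragraph of 9.3 again says PRO score for the ROC variable, which is a change, so the term is loose shorthand there. The supportive paragraph runs its distribution-based work on change data to back up the responder definition, which treats that definition as change-based.

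This stands as evidence of intent. It does not make the classification sentence correct: 9.4 gives score and change separate meanings, and the sentence uses the wrong one.

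A reader might go further and infer that the SAP's rule makes essentially everyone a responder, or that the PRO responder results will be meaningless. The documents do not support that. The outcome arises only if one sentence is programmed apart from its section. The 100% figure is strict for CHQ dyspnea only at thresholds of 1 or less, and the KCCQ-TSS figures depend on an assumed score distribution. Other change-based displays also remain: an empirical distribution function of change by arm (7.5.1.4), and a chi-square test of CHQ domain response defined as an improvement of at least 0.5 points (5.3 and 7.6.1), with dyspnea one of the domains.

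**Conclusion.** The point holds as a defect of wording in an operative rule. The intended rule, change from baseline to week 12 at or above the threshold, is recoverable, so this is a correction to make rather than a flaw in the design.

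The CHQ result in step 2 rests on the scoring range alone, given a threshold of 1 or less. The KCCQ-TSS range rests on the assumed week-12 means, SDs and truncated normal shape. The 0.5 and 5 points are stand-ins from SAP 5.3 for anchor-based thresholds that cannot be known before the data.

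The reach is limited to the exploratory responder analysis in 7.5.1.4, which lies outside the primary test and the Hochberg step. The Wilcoxon tests of the primary and key secondary endpoints are specified on change from baseline and are not affected.

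**What to change.** In the classification sentence of SAP 9.3, insert *the change from baseline to week 12 in* immediately before *the PRO score*, and leave the reference to the PGI-S anchor as it is. In the same edit, say score or change in the sentence that assigns the threshold to each scale, in the description of the ROC curve, and for the medians of CHQ-SAS dyspnea and KCCQ-TSS tabulated by PGI-S category, which are also unspecified.

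The cost is one sentence plus a few words. No analysis, sample size or testing order changes. The edit should be made before unblinding and recorded in the SAP history table.
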